I acknowledge that I am responsible for the overall study conduct. I agree to personally conduct or supervise the described clinical study. I agree to ensure that all associates, colleagues and employees assisting in the conduct of the study at my site are informed about their obligations. Mechanisms are in place to ensure that site staff receive the appropriate information throughout the conduct of the study.

Investigator's Signature

Date

Investigator's Printed Name

SYNOPSIS

TITLE: A Phase 1 Open-Label Single-Ascending Dose Study to Evaluate the Safety, Tolerability, and Pharmacokinetics of OP-101 (dendrimer n-acetyl-cysteine) After Subcutaneous Administration in Healthy Volunteers

PROTOCOL NUMBER: OP-101-003

INVESTIGATIONAL PRODUCT: OP-101 (dendrimer n-acetyl-cysteine)

PHASE: 1

INDICATION(S): Treatment of children with childhood cerebral adrenoleukodystrophy who are not eligible for hematopoietic stem cell transplantation.

OBJECTIVES:

The primary objective is to evaluate the safety and tolerability of OP-101 after single subcutaneous (SC) doses in healthy subjects.

The secondary objective is to determine the pharmacokinetic (PK) profile of OP-101 after single SC doses in healthy subjects.

POPULATION:

The population for this study includes men and women aged 18 to 65 years, inclusive, who are in good health as determined by screening medical history, a physical examination, vital sign measurements, and clinical laboratory tests (chemistry, hematology, and urinalysis). Subjects are to have a body mass index between 18 and 32 kg/m², inclusive.

STUDY DESIGN AND DURATION:

This is a Phase 1, open-label, single-ascending dose study to evaluate the safety, tolerability, and PK of OP-101 after SC administration in up to 8 healthy subjects at 1 site in Australia.

This study will consist of a 21-day Screening Period, a 2-day Treatment Period, and Follow-up Visits on Days 8 and 15. Subjects will sign an informed consent form before any study procedures are performed and must meet all of the inclusion and none of the exclusion criteria to participate in the study. Eligible subjects will be admitted to the investigational site on Day -1, dosed on Day 1, and discharged on Day 3.

There will be 2 separate and sequential SC cohorts (4 mg/kg and 8 mg/kg) with 4 subjects in each cohort who complete Day 15. Cohort 1 will enroll 4 subjects administered a single SC dose of 4 mg/kg. Dose escalation from Cohort 1 (4 mg/kg) to Cohort 2 (8 mg/kg) will be determined by the safety review committee (SRC), consisting of the Medical Monitor, the Principal Investigator (or delegate), and Sponsor representative after review of safety, tolerability, and any available PK data through Day 8 of Cohort 1. Cohort 2 will enroll 4 subjects administered a single SC dose of 8 mg/kg.

During the Treatment Period, plasma and urine samples will be collected for PK analysis. Plasma PK samples will be collected predose, at 30 minutes and at 1, 2, 4, 6, 8, 10, 12, 16, 24, and 30-36 hours after dosing, as well as on Day 3 (~48 hr). Blood samples for PK analysis can be obtained within ± 5 minutes of the scheduled sampling time for sample times ≤ 1 hour, within ± 10 minutes of the scheduled sampling time for sample times ≤ 12 hours, and within ± 2 hours of the scheduled sampling times for sample times > 12 hours.

Urine PK samples will be collected predose (spot sample) and between 0 to 4, 4 to 8, 8 to 12, 12 to 18, 18 to 24, and 24 to 48 hours.

Safety assessments will include adverse event monitoring, clinical laboratory tests (hematology, chemistry, and urinalysis), physical examinations, and vital signs (pulse rate, blood pressure [BP], respiration rate, and temperature). Coagulation testing will be performed at screening. Pregnancy testing will be performed at screening and Day -1.

DOSAGE FORMS AND ROUTE OF ADMINISTRATION:

Subjects in Cohort 1 will be administered 4 mg/kg OP-101 as a SC injection.

Subjects in Cohort 2 will be administered 8 mg/kg OP-101 as a SC injection.

PHARMACOKINETIC VARIABLES:

The PK variables will include the following:

- C_{\max} – maximum plasma concentration,
 - t_{\max} – time to maximum plasma concentration,
 - k_{el} – apparent terminal rate constant,
 - $t_{1/2}$ – apparent elimination half-life,
 - AUC_{0-t} – area under the concentration-time curve based on the last measurable concentration,
 - AUC_{0-inf} – area under the concentration-time curve from time zero to infinity, and
 - CL – clearance of study drug.
-

SAFETY VARIABLES:

Safety assessments will include adverse event monitoring, clinical laboratory tests (hematology, chemistry, and urinalysis), physical examinations, and vital signs (pulse rate, BP, respiration rate, and temperature).

STATISTICAL ANALYSES:

The PK Concentration Population is defined as all subjects who received at least 1 dose of study drug and have at least 1 measurable concentration. The PK Parameter Population is defined as all subjects who received a dose of study drug and have at least 1 PK parameter. Plasma PK concentrations of OP-101 will be summarized with descriptive statistics (n, mean, standard deviation [SD], percent coefficient of variation [%CV], minimum, median, maximum, geometric mean, and %CV for the geometric mean) by nominal PK sampling time and treatment using the PK Concentration Population. Standard noncompartmental PK analysis will be used to calculate the PK parameters. Pharmacokinetic parameters will be summarized with descriptive statistics (n, mean, SD, %CV, minimum, median, maximum, geometric mean, and %CV for the geometric mean) by treatment using the PK Parameter Population.

The Safety Population is defined as all subjects who received at least 1 dose of study drug. Adverse events will be summarized overall and by system organ class and preferred term, and the relationship to the study drug received. A list of subjects who have SAEs and who discontinued from the study due to an adverse event will be provided. Deaths due to adverse events will also be provided. Safety laboratory tests will include chemistry, hematology, and urinalysis. Summary statistics for laboratory values will be provided at baseline, postbaseline, and for changes from baseline to postbaseline by treatment. Occurrence of significant laboratory abnormalities will be summarized by regimen for each treatment. Vital signs will be summarized in the same manner as clinical laboratory evaluations, and physical examination data will be listed.

SAMPLE SIZE DETERMINATION:

Up to 8 subjects will be enrolled and dosed in 2 cohorts with 4 subjects in each cohort who complete Day 15. The sample size in the study is based on clinical and practical considerations rather than statistical power.

SITES: 1 site in Australia.

SPONSOR:

Orpheris, Inc.
[name]
[name]
Telephone: [REDACTED]

TABLE OF CONTENTS

Signature Page	2
Investigator Agreement.....	3
Synopsis	4
Table of Contents.....	7
List of Figures.....	11

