2 STUDY OBJECTIVES

2.1 Primary Objective

The primary objective is to evaluate the safety and tolerability of OP-101 after single SC doses in healthy subjects.

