6.3 Treatment Period (Days 1 to 3)

6.3.1 Day 1

The following procedures will be performed on Day 1:

- Record prior and concomitant medications;
- Record vital signs (predose, 30 and 60 minutes and at 2, 4, and 12 hours after SC dosing);
- Collect urine sample for urinalysis predose;
- Obtain fasting blood sample for safety laboratory tests within 30 minutes prior to dosing;
- Administer study drug;
- Collect plasma PK samples (collected within 30 minutes prior to dosing, and at 30 minutes and 1, 2, 4, 6, 8, 10, 12, and 16 hours);
- Collect urine PK sample (within 60 to 30 minutes prior to dosing [spot sample] and between 0 to 4, 4 to 8, 8 to 12, 12 to 18, and 18 to 24 hours after dosing);
- Assess adverse events.

6.3.2 Day 2

The following procedures will be performed on Day 2:

- Record prior and concomitant medications;
- Perform physical examination;
- Record vital signs at 24 hours;
- Collect urine sample for urinary albumin, urinary creatinine, KIM-1, NGAL and urinalysis at 24 hours;
- Obtain fasting blood sample for safety laboratory tests at 24 hours;
- Collect plasma PK sample (24 and 30-36 hours after dosing);
- Collect urine PK sample (between 24 to 48 hours after dosing); and
- Assess adverse events.

6.3.3 Day 3

The following procedures will be performed on Day 3:

- Record prior and concomitant medications;
- Perform physical examination;
- Record vital signs at 48 hours;
- Collect urine sample for urinary albumin, urinary creatinine, KIM-1, NGAL and urinalysis at 48 hours;
- Collect plasma PK sample (48 hours after dosing);
- Collect urine PK sample up to 48 hours;
- Obtain fasting blood sample for safety laboratory tests at 48 hours;
- Assess adverse events; and
- Discharge subject from the investigational site.

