8.8 Physical Examinations

Complete physical examinations will be performed at screening, on Day -1, Day 2, Day 3, Day 8, and Day 15, or at the Early Termination Visit. Body weight and height will be measured at screening and used to calculate BMI.

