APPENDIX A: SCHEDULE OF PROCEDURES

Table 1. Schedule of Procedures – Cohorts 1 and 2

Study Procedure	Screening Period	Check-In	Treatment Period			Follow-Up Visits [1]		Early Termination Visit
			Day 1	Day 2	Day 3	Day 8	Day 15	
Informed consent	Days -21 to -2	Day -1						
Admit to investigational site	X							
Inclusion/exclusion criteria	X	X						
Medical history	X							
Demographics	X							
Prior/concomitant medications	X	X	X	X [3]	X	X	X	X
BMI calculation [2]	X							
Physical examination (complete)	X	X	X	X [3]	X	X	X	X
Vital signs [4]	X	X	X	X [3]	X	X	X	X
Breath alcohol screen	X	X						
Pregnancy test [5]	X	X						
FSH [5]	X							
Urine drug and cotinine screen	X	X						
Safety	X	X	X	X [3]	X	X	X	X

laboratory tests (chemistry, hematology, and urinalysis) [6]													
aPTT, PTT, INR	X												
HIV, HBsAg, HCVab screen	X												
Plasma PK sampling [7]					X		X						
Urine PK sampling [8]					X		X						
Administer study drug [9]					X								
Assess adverse events	X				X				X[3]		X		X
Discharge from investigational site									X				

Footnotes appear on the following page.

A 30-minute window for vital signs and all postdose procedures is allowed.

When multiple procedures are scheduled at the same time point, the order of procedures should be as follows: obtain vital signs, collect blood sample (drawn at nominal time), and obtain urine sample.

1. There will be a \pm 1-day visit window for Days 8 and 15.
2. Body weight and height will be measured at screening and used to calculate BMI.
3. Assessments will be performed prior to discharge.
4. Vital signs (pulse rate, respiration rate, body temperature, and BP) will be recorded at all study visits after the subject has been seated or supine for \geq 5 minutes. During the Treatment Period, vital signs will be measured predose, 30 and 60 minutes and at 2, 4, 12, 24 and 48 hours after SC dosing.
5. A serum (beta HCG) pregnancy test will be performed at screening for female subjects of childbearing potential only. A urine pregnancy test will be performed at Day -1 for female subjects of childbearing potential only. A test for FSH level will be performed only for women of non-childbearing potential who are not surgically sterile.

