## 5.2 Safety Variables

The following safety evaluations will be performed during the study:

- Adverse event monitoring
- Vital signs (pulse rate, BP, respiration rate, and temperature).
- Physical examination
- Clinical laboratory tests (hematology, chemistry, and urinalysis)

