#### **7.4.4 Physical Examination**

Complete physical examinations will be performed at screening, on Day -21 to -2, Day -1, Day 2, Day 3, Day 8 and Day 15, or at the Early Termination Visit. Body weight and height will be measured at screening and used to calculate BMI.

Physical examination data will be listed by treatment for the Safety Population.

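### SC tolerability is part of the primary objective, but no standardised, timed, solicited injection-site assessment or local-tolerability summary is planned, so short-lived local reactions may be missed or inconsistently recorded and graded.

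*Protocol*

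**What the plan says.** Protocol Section 2.1 reads: "The primary objective is to evaluate the safety and tolerability of OP-101 after single SC doses in healthy subjects". Protocol Sections 1.1 and 1.2 report that single IV doses of 20 and 40 mg/kg have already been given to healthy subjects. Section 5.5.1 describes the SC product as 400 mg/mL after reconstitution.

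The safety measurements are general ones. The protocol synopsis says "Safety assessments will include adverse event monitoring, clinical laboratory tests (hematology, chemistry, and urinalysis), physical examinations, and vital signs". SAP Section 5.2, under "The following safety evaluations will be performed during the study", lists AE monitoring, vital signs, physical examination and laboratory tests. Neither list has an injection-site item.

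On examinations, Protocol Section 8.8 says "Complete physical examinations will be performed at screening, on Day -1, Day 2, Day 3, Day 8, and Day 15" (or at early termination), and SAP Section 7.4.4 says "Complete physical examinations will be performed at screening, on Day -21 to -2, Day -1, Day 2, Day 3, Day 8 and Day 15". Neither names Day 1, and the Day 1 procedures in Protocol Section 6.3.1 include no physical examination. Timed Day 1 contacts do exist: "Record vital signs (predose, 30 and 60 minutes and at 2, 4, and 12 hours after SC dosing", and plasma PK draws "at 30 minutes and 1, 2, 4, 6, 8, 10, 12, and 16 hours". AE assessment is a Day 1 item with no times attached.

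**The concern.** The systemic safety of the molecule has IV data behind it at doses above those planned here. Local tolerance of a concentrated SC injection does not, and it is what a sponsor considering chronic SC dosing (Protocol Section 5.2) most needs to learn from these 8 subjects. Pain, redness, swelling and induration can appear and fade within hours. If nobody is told to look at and grade the site at set times, what reaches the database depends on what the subject mentions and what staff happen to notice and write down.

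Two uses of the data are exposed. The safety review committee weighs tolerability before escalating to Cohort 2. The stopping rule in Protocol Section 3.2 counts drug-related Grade 2 events within a cohort. With 4 subjects per cohort, each subject is 25 percentage points of the observed reaction rate.

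**Working it through.** **1. The plan's own figure.** The sample size is 2 cohorts × 4 = 8, which agrees with Protocol Section 9.3. It rests on practical grounds, so there is no assumed event rate or power to reproduce.

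**2. Search for a local-tolerability measurement.**
- Safety lists (Protocol Synopsis and Section 3.1; SAP Sections 3.3 and 5.2): none.
- Day 1 to Day 15 procedures (Protocol Sections 6.3 to 6.5): none. The order of procedures at a shared time point in Section 6 is vital signs, blood, urine.
- AE tables (SAP Section 7.4.1.2): by system organ class, preferred term, severity and relationship, with no dedicated local-reaction summary.
- Physical examination (Protocol Section 9.2.3.4; SAP Section 7.4.4): findings are listed only, not summarised.

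By contrast, the renal signal has its own timed markers (KIM-1 and NGAL on Days -1, 2, 3, 8 and 15).

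**3. Day 1 examination: text against table.** Protocol Sections 6.3.1 and 8.8 and SAP Section 7.4.4 omit Day 1. In the protocol's Appendix A as extracted, the row "Physical examination (complete") carries eight marks for eight visit columns, the same pattern as vital signs, which are taken on Day 1. The table is visibly broken: the footnote for assessments before discharge falls in the Day 2 position, although discharge is on Day 3. The SAP table is less reliable still, with three marks for screens that the SAP text limits to two visits. Neither table gives a predose or postdose time for a Day 1 examination.

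**4. Timed contacts already in place.** Day 1 has nine postdose PK draws (30 min; 1, 2, 4, 6, 8, 10, 12 and 16 h). Vital signs coincide with five of them (30 and 60 min; 2, 4 and 12 h). Adding 24 h, 48 h, Day 8 and Day 15 gives 5 + 2 + 2 = 9 postdose vital-sign contacts per subject.

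**5. What incomplete capture would do (illustration).** Let p be the true reaction rate per subject and c the share recorded. Both are assumed; the documents give neither. With q = p × c:

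- P(none recorded in 4) = (1 − q)^4
- P(2 or more recorded in 4) = 1 − (1 − q)^4 − 4q(1 − q)^3

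| p | c | q | Expected recorded of 8 | P(none of 4) | P(2 or more of 4) |
|---|---|---|---|---|---|
| 0.25 | 1 | 0.25 | 2.0 | 0.316 | 0.262 |
| 0.25 | 0.5 | 0.125 | 1.0 | 0.586 | 0.079 |
| 0.50 | 1 | 0.50 | 4.0 | 0.063 | 0.688 |
| 0.50 | 0.75 | 0.375 | 3.0 | 0.153 | 0.481 |
| 0.50 | 0.5 | 0.25 | 2.0 | 0.316 | 0.262 |
| 0.75 | 1 | 0.75 | 6.0 | 0.004 | 0.949 |
| 0.75 | 0.5 | 0.375 | 3.0 | 0.153 | 0.481 |

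For example, at p = 0.50 with full capture, 0.5^4 = 0.063; with half capture, 0.75^4 = 0.316. The last column bears on the stopping rule only if the reactions are Grade 2 and judged drug-related.

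**6. Two features that make general AE data harder to read.** Protocol Section 8.1.3 grades by CTCAE Version 5.0 and SAP Section 7.4.1 by Version 4.0. The number of injections may also differ between cohorts. Protocol Section 5.2 puts one injection at 400-500 mg, which 8 mg/kg reaches at 400/8 = 50 kg to 500/8 = 62.5 kg, and 4 mg/kg at 400/4 = 100 kg to 500/4 = 125 kg. Without per-site data, a difference by dose cannot be separated from a difference in injections.

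**The case against.** The best defence is that local reactions are already within data capture. Subjects are resident from Day -1 to Day 3. AEs are assessed on Days 1, 2, 3, 8 and 15, and Protocol Section 8.1 requires recording of problems that staff observe as well as those subjects raise. Staff meet each subject at nine timed draws in the first 16 hours. This stands. A reader might infer that local reactions will be under-counted, or that nobody is looking for them; the documents show neither. They show only that the looking is not prompted, timed or standardised.

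A reader might also infer that no examination takes place in the first 24 hours. The text lists none on Day 1, but the protocol table appears to mark one. The Day 2 examination has no clock time, so it could fall before 24 hours.

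Nor does it follow that the two doses cannot be compared. Recorded injection-site terms would appear in the SAP tables by treatment and maximum severity, and with 4 per cohort any comparison is descriptive.

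Finally, the eCRF and the output specifications are separate documents that were not available. The AE page may already carry a site prompt. If it does, the protocol and SAP should say so.

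**Conclusion.** The gap is real and confined to measurement: no standardised, timed, solicited injection-site assessment and no local-tolerability summary, in a study whose primary objective includes SC tolerability. Short-lived reactions may be missed, or recorded and graded inconsistently.

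The size cannot be derived from the documents. If the true rate were 50% and half of reactions were captured, the chance of an apparently clean cohort of 4 would rise from 6% to 32%; across assumed true rates of 25% to 75%, half capture moves it from 32% to 59% at the low end and from under 1% to 15% at the high end. These figures show why capture matters at n = 4. They do not show that capture is poor.

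This is a worthwhile, low-cost improvement to how the primary objective is measured, not a demonstrated failure of that objective. Separately, the procedure text and the schedule table should be reconciled on whether a Day 1 physical examination is done and, if so, when.

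**What to change.** At the existing postdose vital-sign times (30 and 60 min; 2, 4, 12, 24 and 48 h) and at the Day 8 and Day 15 visits, record on the eCRF a graded injection-site check covering pain, redness, swelling and induration. Record it per site if more than one injection is given. Add the variable to SAP Section 5.2, and to Section 7.4 a table by cohort with counts, maximum grade and time of onset. Align the Day 1 examination entry across Protocol Sections 6.3.1 and 8.8, Appendix A and SAP Section 7.4.4.

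The sponsor should also state how solicited readings relate to AE reporting: which become AEs, on which CTCAE version, and whether they feed the events counted in Protocol Section 3.2.

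Cost: a short amendment, one eCRF page, one table and a few staff minutes at each of 9 contacts per subject (9 × 8 = 72 checks if each subject has one site). There is no extra visit, sample or subject, and N stays at 8. The main downside is that solicited checks will probably bring more mild reactions into the record, which the report should explain when these results are set beside data collected without solicitation.

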SAE	Serious adverse event
SD	Standard deviation
SRC	Safety review committee
$t_{1/2}$	Apparent elimination half-life
TGA	Therapeutic Goods Administration
t_{max}	Time to maximum plasma concentration

1 INTRODUCTION AND BACKGROUND INFORMATION

OP-101 is a new chemical entity consisting of a metabolically stable inactive dendrimer covalently coupled to n-acetyl-cysteine (NAC). Upon intravenous (IV) administration, OP-101 is selectively taken up by reactive microglia and reactive astrocytes in the brain through fluid phase endocytosis. The active component of OP-101, NAC, is released upon uptake into reactive microglia and astrocytes. Upon intracellular release from OP-101, NAC acts to reduce oxidative stress and neuroinflammation in the brain. Following release of NAC, the dendrimer component is excreted from the cells and cleared without further metabolism.

Specifically, OP-101 consists of a generation-4 hydroxyl-terminated polyamidoamine (PAMAM) dendrimer linked to NAC using a disulfide bond. PAMAM is a class of dendrimer made of repetitive reactions of methyl acrylate and ethylene diamine. The PAMAM dendrimer contains an ethylene diamine core, amidoamine repeat units ($[\text{CH}_2\text{CH}_2\text{CONHCH}_2\text{CH}_2\text{N}]$), and 64 hydroxyl end groups (chemical formula: $\text{C}_{622}\text{H}_{1184}\text{N}_{186}\text{O}_{188}$). Approximately 20 of the 64 hydroxyls are subsequently converted to amine groups and then to a thiol group for eventual conjugation with NAC using a disulfide bond. The active metabolite of OP-101, NAC, comprises approximately 16% of the total mass of OP-101.

In vitro and in vivo nonclinical studies have demonstrated that the PAMAM dendrimer is metabolically stable and rapidly excreted via the kidney. Upon IV administration, OP-101 is endocytosed by reactive microglia and astrocytes in animal models of neuroinflammation. After endocytosis, the reducing environment inside these cells results in release of NAC and a normalization of glutathione (GSH) levels. As the active metabolite of OP-101, NAC reduces oxidative stress and related proinflammatory cytokines (via the nuclear receptor, $\text{NF}\kappa\beta$ pathway), decreasing neuroinflammation and central nervous system (CNS) toxicity. Pharmacology studies support the specific targeting of OP-101 to microglia and the intracellular release of NAC (Kurtoglu 2009; Navath 2008), as well as the ability of OP-101 to significantly reduce a proinflammatory response as compared with unconjugated free NAC (Dai 2010; Kambhampati 2015; Kannan 2012; Lesniak 2013; Mishra 2014; Nance 2015; Nemeth 2017).

NAC, the active metabolite of OP-101, is an approved product and marketed under Acetadote[®], and the putative mechanism of action of OP-101 is related to the chemical and biological properties of NAC. NAC has been approved for use as a mucolytic agent and for the treatment of acetaminophen intoxication in addition to other conditions and disorders, including doxorubicin-induced cardiotoxicity, radio-contrast-induced nephropathy, and chemotherapy-induced toxicity (Samuni 2013). NAC has been shown to interact with several metabolic pathways including regulation of cell cycle and apoptosis, but the main clinical effect of NAC is attributed mainly to its ability to scavenge reactive oxygen species (ROS) and elevate cellular GSH levels. NAC is recognized to suppress microglial activation (Tsai 2009) and inhibit $\text{NF}\kappa\text{B}$ -mediated proinflammatory cytokines by macrophages and glial cells (Pahan 1998). Examples of CNS effects of NAC include reduced levels of proinflammatory cytokines tumor necrosis factor-alpha, interleukin (IL)-1beta in rodent models of traumatic brain injury and cerebral ischemia (Chen 2008; Khan 2004), and IL-6 and IL-10 in lipopolysaccharide-treated rat fetal brain (Beloosesky 2012). The human safety profile for NAC, based on the collective experience with Acetadote, supports human testing of OP-101.

OP-101 is being developed as a possible treatment for patients with advanced childhood cerebral adrenoleukodystrophy (ccALD) who are not considered eligible for hematopoietic stem cell

transplantation (HSCT). Adrenoleukodystrophy (ALD) is an X-linked disease caused by mutations in the *ABCD1* that result in oxidative stress and neuroinflammation in several critical CNS cell types (Deon 2016). The disease affects cerebral white matter, spinal cord, and peripheral nerves, with some pediatric phenotypes suffering rapid progression leading to death in early childhood (Moser 2000; Moser 2007). About 35% of all hemizygous males between 3 and 10 years of age develop a form of ALD that manifests with progressive neuroinflammation resulting in widespread demyelination and rapid neurological deterioration. This phenotype is referred to as ccALD and typically leads to death within 2 to 5 years after onset of symptoms. While HSCT may stabilize patients in the very early stages of ALD, there is no effective therapy for patients who present with advanced stages of ccALD where HSCT is contraindicated. Therefore, OP-101 is being investigated as a potential treatment for patients with advanced ccALD who present with signs of progressive neuroinflammation potentially reversible by OP-101 and who are not candidates for HSCT.

